5.1.2 Screening Phase

After providing consent to participate, patients with a deleterious BRCA1/2, ATM, or other HRR gene mutation will undergo Screening assessments within 28 days prior to the first dose of rucaparib. Patients will undergo procedures and assessments during Screening Phase as described in [Section 9.4](#).

During the Screening Phase, unless otherwise required by local regulations, serious adverse events (SAEs) which are related to protocol-mandated assessments will be reported.

Additional screening assessments will include collection of the patient's medical information and demographics, physical exam, laboratory safety assessments, tumor assessments, PRO instruments, and blood and tissue samples to support exploratory objectives as described in [Section 9.4](#).

Enrollment will require prospective sponsor (or designee) review and confirmation of eligibility, including, but not limited to:

- BRCA/ATM/other HRR gene test result by either local or central testing
- details of prior therapy for prostate cancer
- screening laboratory assessments

5.1.3 Treatment Phase

Rucaparib will be administered at a starting dose of 600 mg BID. During the Treatment Phase, patients will undergo procedures and assessments including regular evaluations for safety and efficacy as described in [Section 9.5](#).

Tumor assessments by CT/MRI and bone scans will be performed during screening, at the end of every 8 calendar weeks (± 7 days) from Study Day 1 (Week 1) up to 24 weeks and every 12 calendar weeks (± 7 days) thereafter, and at the Treatment Discontinuation Visit, if applicable. Modified RECIST Version 1.1 criteria will be used to document radiologic response in soft tissue (visceral and nodal) disease and PCWG3 criteria will be used to document radiologic progression in bone lesions. If a CR or PR is noted, confirmatory scans should be performed at least 4 weeks after the initial response was first documented. Any drug modifications (interruption, dose reduction, or discontinuation) should be documented in the eCRF and source documents. If study treatment is interrupted, tumor assessments will not be delayed and will be performed on the regular study schedule. Copies of all radiologic scans will be collected for central independent radiology review (IRR).

Patients will receive rucaparib until confirmed radiologic disease progression assessed by investigator based on modified RECIST Version 1.1 and/or PCWG3 (for bone lesions only) criteria, unequivocal clinical disease progression, unacceptable toxicity or inability to tolerate further treatment, loss to follow-up; or withdrawal of consent. PSA rise without evidence of confirmed radiologic progression is strongly discouraged as a criterion to start a new systemic antineoplastic therapy during the first 12 weeks of therapy and is discouraged as a criterion to start a new systemic antineoplastic therapy throughout the study. Palliative radiation for treatment of painful bony metastases and initiation of bisphosphonates or other approved bone-targeting agents are allowed and should not result in discontinuation of study drug therapy. Patients who discontinue study treatment for reasons other than radiologic disease progression, should continue radiologic tumor assessment performed as described in [Section 5.1.4](#).

If a patient has radiologic progression, but continues to derive clinical benefit per the investigator, then continuation of treatment beyond progression may be requested by the investigator as per [Section 7.4.4](#). In such cases, the decision to continue will be made jointly between the investigator and the sponsor (or designee), and the patient must consent prior to continuing treatment with rucaparib. These patients will continue to undergo all protocol required assessments specified in [Table 5](#).

Patient safety will be monitored on a regular basis using procedures and assessments described in [Section 9](#) and [Section 13.4](#). Safety data will be periodically reviewed by the Data Monitoring Committee (DMC) as described in [Section 13.6](#). The DMC will comprise study investigators and sponsor representatives. The DMC will meet after the first 20 patients received rucaparib for at least 28 days or discontinued study treatment, and then at least semi-annually after sufficient data has been collected.

5.1.4 Post-treatment Phase

The sponsor (or designee) should be notified of all treatment terminations as soon as possible. The date and reason for cessation of study drug must be documented in the eCRF and source documents. Patients will undergo procedures and assessments during the Post-treatment Phase as described in [Section 9.6](#). Upon treatment discontinuation, patients will have a Treatment Discontinuation Visit ([Section 9.6.1](#)), a 28-Day Follow-up Visit ([Section 9.6.2](#)), and then will proceed to long-term follow-up ([Section 9.6.3](#)). An optional tumor biopsy will be collected prior to the start of subsequent anticancer therapy from patients who experience radiographic or unequivocal clinical disease progression and who provide appropriate consent. For patients who had their last tumor assessment ≥ 8 weeks (≥ 12 weeks if previous scan was after 24 weeks on study) prior to Treatment Discontinuation Visit, a tumor assessment must be performed.

If treatment was discontinued for reasons other than radiologic disease progression, radiologic tumor assessment (using the same methodology as was used at initial study screening [eg, CT scan]) and PRO assessments will continue until confirmed radiographic disease progression. For these patients, tumor assessments should continue to be performed at the end of every 8 calendar weeks (± 7 days) relative to Study Day 1 (Week 1) up to 24 weeks and then every 12 calendar weeks (± 7 days) thereafter, until confirmed radiologic disease progression by modified RECIST Version 1.1 and PCWG3 (for bone lesions only) criteria as assessed by the investigator, loss to follow-up, withdrawal of consent, or study closure. For patients who start subsequent

anticancer therapy, tumor assessments will continue until radiologic disease progression is confirmed.

Ongoing SAEs, AESIs, and treatment related Grade 3/4 AEs will be followed until either resolution or stabilization has been determined or until loss to follow-up. After the 28-Day Follow-up Visit, only SAEs considered as potentially related to study drug should be reported per Clovis Pharmacovigilance (PV) requirements and captured in the Clovis PV database. This includes serious reports of pneumonitis or associated events, if considered to be related to study drug.

After the 28-day Follow-up Visit, AESIs of MDS and AML, irrespective of causality, should be reported per Clovis PV requirements and captured in the Clovis PV database.

- AESIs of pneumonitis or associated events should only be reported up to, but not beyond, the 28-Day Follow-up Visit (28-days after the last dose of rucaparib).

[figure not shown]
All patients will be followed for survival and subsequent treatments every 12 weeks (\pm 14 days) relative to the last dose of rucaparib until death, loss to follow-up, withdrawal of consent, or study closure.

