- ^k = Disease assessment by CT/MRI and bone scans will be performed during screening, during the treatment phase, and Treatment Discontinuation, and if applicable, during follow up. Modified RECIST 1.1/PCWG3 criteria will be used. If a CR or PR is noted, confirmatory scans should be performed at least 4 weeks after the initial response was first documented.

- ^l = Radiologic assessments should continue for all patients until confirmation of radiographic progression per investigator assessment, including any patient who discontinued from study treatment for reason other than disease progression or death. Tumor assessments should be performed during the Treatment Discontinuation visit, 28-day Follow-up, or during Long-term Follow-up if the reason was other than radiologically confirmed disease progression and it has been ≥ 8 weeks (≥ 12 weeks if previous scan was after 24 weeks on study) since the last assessment. Tumor assessments should continue on schedule (ie, every 8 or 12 weeks) during Long-term Follow-up until radiographically confirmed disease progression.
- ^m = If archival primary or metastatic tumor tissue was not submitted during Pre-Screening, a specimen should be submitted during the Screening period or after enrollment for retrospective testing by the central laboratory. Archival tissue submitted during Screening for retrospective testing can be > 3 years old. Refer to the Pathology Charter for detailed sample handling instructions.
- ⁿ = The BPI-SF, analgesic drug score, FACT-P, and EQ-5D-5L instruments should be completed prior to other scheduled study procedures and dosing (if applicable). During long term follow up, if possible, PROs to be collected to coincide on days when tumor assessments are performed.
- ^o = All PSA measurements are performed by the local laboratory. Serial PSA measurements that show progression at study entry must follow the protocol specification.

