12 PATIENT DISPOSITION

12.1 Removal of Patients from the Study or Study Drug

A patient must be discontinued from protocol prescribed- therapy if any of the following apply:

- Consent withdrawal for any reason at the patient's own request or at the request of their legally authorized representative;
- Radiographic progression of patient's underlying cancer per modified RECIST Version 1.1/PCWG3 (unless, in the opinion of the investigator, the patient continues to derive clinical benefit; treatment beyond progression is permitted with additional consent);
- Unequivocal clinical progression of the patient's underlying cancer that in the opinion of the investigator requires immediate change in systemic anticancer therapy, or results in marked deterioration in ECOG performance status to Grade 3 or higher
- Any event, adverse or otherwise, that, in the opinion of the investigator, would pose an unacceptable safety risk to the patient;
- An intercurrent illness that, in the opinion of the investigator, would affect assessments of the clinical status to a significant degree and requires discontinuation of therapy;
- Noncompliance by the patient with protocol mandated procedures

Discontinuation of treatment does not necessarily indicate study discontinuation for a patient. Samples collected for research will continue to be used unless the patient explicitly withdraws consent for their use. If the patient withdraws consent to continue in the study or discontinues the study for another reason it will be documented on the appropriate eCRF. A patient may withdraw consent to participate in an additional part of a study that has an additional consent (ie, optional tumor biopsy) yet continue to participate and be treated/ followed in the main part of the study.

The sponsor may discontinue the trial early for any of the reasons noted in [Section 13.7](#).

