PCWG3 Criteria for Confirmation of Radiographic Progression in Bone by Investigator Assessment (to be used in conjunction with modified RECIST 1.1 criteria for visceral and nodal disease)

Date Progression Detected (Visit)	Criteria for Progression in Bone	Criteria for Confirmation of Progression in Bone
Week 9 (1 st on-treatment scan)	Two or more new lesions on bone scan compared to baseline bone scan by PCWG3	Two or more new bone lesions identified at Week 9 must persist at Week 17 and 2 or more additional new lesions must be identified on Week 17 bone scan (compared to Week 9 scan)
Week 17 (2 nd on-treatment scan)	Two or more new lesions on bone scan compared to Week 9 bone scan.	Two or more new lesions identified at Week 17 must persist at Week 25 bone scan
Week 25 and after (3 rd on-treatment scan and after)	Two or more new lesions on bone scan compared to Week 9 bone scan	Two or more new lesions identified at Week 25 (or later) bone scan must persist at scan obtained 6 weeks later

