Rucaparib will be administered at a starting dose of 600 mg BID until disease progression as assessed by the investigator based on modified RECIST Version 1.1¹ and/or PCWG3² (for bone lesions only) criteria, or other reason for discontinuation. Patients may continue to receive rucaparib beyond progression if agreed upon by the investigator and sponsor. Tumor assessments by CT, MRI, PET/CT, and/or bone scans will be performed during screening, at the end of every 8 calendar weeks (± 7 days) from Study Day 1 (Week 1) up to 24 weeks and every 12 calendar weeks (± 7 days) thereafter, and should be performed at the time of treatment discontinuation, at the 28-day Follow-up visit, or during Long-term Follow-up if the reason was other than radiologically confirmed disease progression and it has been ≥ 8 weeks (≥ 12 weeks if previous scan was after 24 weeks on study) since the last assessment. Tumor assessments should continue on schedule (ie, every 8 or 12 weeks) during Long-term Follow-up until radiographically confirmed disease progression by modified RECIST v1.1 and/or PCWG3 criteria. Copies of all radiographic scans will be collected for central independent radiology review (IRR).

Figure 1: Pre-Screening Study Schema.

* Patients should be demonstrating radiographic or biochemical progression in order to enter the Pre-Screening and Screening Phases
** Metastatic biopsy (preferred) or archival tissue; tissue samples should be < 3 years old

Figure 2: Study Schema - Screening, Treatment, and Post-treatment Phases.

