10.2.2 Radiographic PFS

rPFS is defined as the time from first dose of rucaparib to the date of first objective evidence of radiographic progression (soft tissue or bone lesion) or death due to any cause, whichever occurs first, plus 1 day. Radiographic disease progression includes confirmed bone disease progression and soft tissue disease progression adjudicated by IRR using the PCWG3 guidelines for bone disease and modified RECIST Version 1.1 for soft tissue disease. Patients without a documented event of progression will be censored on the date of their last adequate tumor assessment (i.e., radiographic assessment) or date of first dose of study drug if no post-baseline tumor assessments have been performed.

Patients who withdraw from treatment prior to radiographic progression will be followed for disease status and survival whenever possible. Only tumor scans (and deaths, for PFS analyses) prior to start of any subsequent anticancer treatment will be included. If a patient discontinues study drug due to a reason other than radiographic PD and subsequently begins another anticancer therapy (ACT) prior to a PFS event, that patient will be censored at the last scan prior to the start of ACT. However, scans/PFS events occurring more than 24 weeks after DC/stop of study drug and more than 24 weeks after their last previous scan but prior to start of subsequent ACT will not be included in the analysis and such patients will be censored at their last scan prior to the end of the 24-week window.

rPFS will be presented by gene mutation for all patients (separately, using IRR and Investigator assessments) and may also be presented by measurable disease status at Baseline.

A sensitivity analysis will be performed in which patients who have discontinued without radiographic progression, but who have had PSA progression, will be treated as having an event at the time of PSA progression.

rPFS will be summarized using Kaplan-Meier methodology and in the case of a low censoring rate it may be summarized with descriptive statistics.

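### The documents disagree on whether radiologic progression must be confirmed before treatment stops and before scans end; under one permitted reading, unconfirmed first-scan bone lesions become a censored rPFS time

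*Protocol*

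**What the plan says.** **Stopping treatment.** Protocol 5.1.3 reads "Patients will receive rucaparib until confirmed radiologic disease progression assessed by investigator". Protocol 7.4.4 and the synopsis (Treatment Discontinuation Criteria) also require confirmation. Protocol 12.1, which is likewise a list of mandatory reasons to discontinue, names radiographic progression of the "underlying cancer per modified RECIST Version 1.1/PCWG3 (unless, in the opinion of the investigator" judges that the patient still benefits. The word *confirmed* is absent. SAP 2.2 also omits it: "600 mg BID until disease progression as assessed by the investigator based on modified RECIST".

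**Scanning after stopping.** Protocol 5.1.3 ends with "Patients who discontinue study treatment for reasons other than radiologic disease progression, should continue radiologic tumor assessment", and 5.1.4 opens its follow-up rule with "If treatment was discontinued for reasons other than radiologic disease progression, radiologic tumor assessment". The synopsis (Post-treatment Phase) and 9.6.3 set a similar condition, again without *confirmed*. On the other side, Table 5 footnote l says "Radiologic assessments should continue for all patients until confirmation of radiographic progression per investigator assessment". Protocol 9.6.1, 9.6.2 and 9.9, the synopsis (Efficacy Assessments) and SAP 2.2 exempt a patient only when progression has been confirmed.

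**Confirmation in bone.** The Appendix 2 table has one column for progression and another for its confirmation. For the first scan, "Two or more new bone lesions identified at Week 9 must persist at Week 17", and two or more additional new lesions must appear on the Week 17 scan (the 2+2 rule). If the rule is met, Appendix 2 dates progression to the first post-treatment scan.

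**Analysis.** SAP 10.2.2 states "Radiographic disease progression includes confirmed bone disease progression"; soft-tissue progression carries no such condition. A patient without an event is censored at the last adequate tumor assessment. Scans and deaths after the start of new anticancer therapy are not used, and a 24-week window limits late events.

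**The concern.** Bone progression on the first scan can count in rPFS only if a second bone scan exists. Some passages end treatment, and scanning with it, at progression that has not been confirmed. If a site follows those passages, the second scan is not scheduled. The same disease course is then an event dated Week 9 at one site and a censored time at Week 9 at another, depending on which section each site applied.

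Such censoring would be informative, because it falls on patients with new bone lesions at the first scan. It would lengthen rPFS by investigator and by IRR alike, since neither reader has a confirming scan to read. Cohort B, which has no measurable soft-tissue disease at entry, is where bone-only findings are most likely to decide the outcome. The only rPFS sensitivity analysis in SAP 10.2.2 is based on PSA progression, so it reaches such a patient only if his PSA has also progressed.

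**Working it through.** The documents give no event count, power or assumed median for rPFS, so there is no planned figure to reproduce. The check has three parts.

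**1. The passages side by side**

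| Question | *Confirmed* required | *Confirmed* absent |
|---|---|---|
| When treatment stops | Synopsis, 5.1.3, 7.4.4 | 12.1, SAP 2.2 |
| Who is exempt from later scans | Synopsis (Efficacy Assessments), Table 5 footnote l, 9.6.1, 9.6.2, 9.9, SAP 2.2 | Synopsis (Post-treatment Phase), 5.1.3, 5.1.4, 9.6.3 |

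Section 9.6.3 also has a clause about progression having been seen on the last scan. It can be read as calling for a rescan in that case, but its *and*/*or* structure leaves this open.

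**2. Does the visit calendar supply the scan anyway?**

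Inputs: first scan at Week 9 (Day 57); 28-Day Follow-up Visit 28 (±3) days after the last dose; a scan at that visit only if at least 8 weeks have passed since the last one. Stopping on Day 57 to 71 is my assumption.

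- Last dose on Day 57: visit on Day 85, which is (85 − 57)/7 = 4.0 weeks after the scan.
- Last dose on Day 71: visit on Day 99, which is (99 − 57)/7 = 6.0 weeks after the scan, or (102 − 57)/7 = 6.4 weeks with the +3-day window.

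The 8-week trigger is not met. The confirming scan at Week 17 (Day 113) therefore falls in long-term follow-up, where 9.6.3 and footnote l disagree.

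**3. Illustrative size**

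Assumptions, none of them from the documents: exponential rPFS with a 26-week median; a fraction q = 0.20 to 0.40 of first-scan progressors have bone-only findings, stop unconfirmed and are never rescanned; all are true progressors; no flare and no later deaths counted.

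- Hazard: λ = ln 2/26 = 0.02666 per week.
- S(8) = exp(−8λ) = 0.808, so p = 1 − 0.808 = 0.192 progress by the first scan.
- Share of all patients affected: p × q = 3.8% to 7.7%, or about 4-8%.
- Kaplan-Meier after the first scan: S′(8) = 1 − p(1 − q) = 0.846 (q = 0.20) or 0.885 (q = 0.40).
- Every later estimate is multiplied by S′(8)/S(8) = 1.048 or 1.095.

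| | All counted as events | q = 0.20 | q = 0.40 |
|---|---|---|---|
| S(24 weeks) | 52.7% | 55.2% | 57.8% |
| S(48 weeks) | 27.8% | 29.1% | 30.5% |

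A simulation of 200,000 patients on the protocol scan schedule gave 55.1% and 57.7% at 24 weeks, and 29.1% and 30.3% at 48 weeks.

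The direction is the same with medians borrowed from other treatments described in Protocol 3.3.1 and 3.5 (4.5, 7.2 and 9.8 months) and q from 10% to 50%. Using median′ = 8 + ln(2S′(8))/λ in weeks, the apparent medians become 4.7-5.5, 7.4-8.2 and 10.0-10.8 months.

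**The case against.** The strongest reply is that the plan, read as a whole, already requires the scan. Footnote l covers all patients, and 9.6.1, 9.6.2, 9.9 and SAP 2.2 exempt only confirmed progression. Section 5.1.4 itself sends the reader to Section 9.6 and says that patients who start new therapy are scanned until progression is confirmed. Further, 12.1 refers to progression per PCWG3, and the Appendix 2 text on following bone progression builds the 2+2 rule into that concept. On this view two lesions at Week 9 are not yet progression, and 12.1 does not permit a stop on them.

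Much of this stands. A reader might infer that early bone progressors are not rescanned and are routinely censored. The documents do not support that, because most passages on later scans point the other way. Nor is censoring automatic even without the scan: soft-tissue progression needs no confirmation, and a death before new therapy and within the 24-week window is an event. It would also be too strong to say that the Week 9 scan showed progression. It showed lesions that may be flare, which is why the 2+2 rule exists.

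What does not fall away is the conflict itself. The Appendix 2 table lists two new Week 9 lesions under progression, separately from confirmation, so a literal reading of 12.1 with 5.1.4 is available. With about 150 sites, differing practice is foreseeable.

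**Conclusion.** The point holds as an internal contradiction with a conditional effect on a secondary endpoint. The documents require confirmation in some places and not in others, both for stopping treatment and for ending scans. Under one permitted reading, a patient stopped on unconfirmed first-scan bone lesions has no Week 17 scan, the 2+2 rule can be neither met nor refuted, and SAP 10.2.2 censors him at the scan that first showed the lesions, subject to the exceptions for soft-tissue progression and death.

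The bias exists only if some of these patients are true progressors, and its size is unknown. The factor of 1.05-1.10 is an upper figure for the assumed 4-8% of patients, because any flare or any later qualifying death would reduce it.

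A reader might infer that the efficacy conclusion is at risk. It is not: rPFS is summarised by Kaplan-Meier without a test, and neither the primary endpoints nor the two-stage decision rules use it. A reader might also infer that restoring the scan is enough. It is not: if new therapy starts before Week 17, SAP 10.2.2 discards the confirming scan and the patient is still censored at Week 9.

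**What to change.** 1. **Scan wording.** Reconcile the synopsis (Post-treatment Phase), 5.1.3, 5.1.4 and 9.6.3 with Table 5 footnote l, 9.6.1, 9.6.2 and 9.9, so that every passage states one condition for ending scans. Resolve the ambiguous clause in 9.6.3 at the same time.
2. **Treatment-stopping wording.** Reconcile 12.1 and SAP 2.2 with the synopsis, 5.1.3 and 7.4.4. Which rule applies is for the sponsor to decide.
3. **SAP 10.2.2.** Add a sensitivity analysis in which unconfirmed bone progression with no later evaluable bone scan counts as an event on the date of the scan that first showed the lesions. Include patients whose confirming scan is excluded because new anticancer therapy had started. Report the result as a lower bound on rPFS, since some of these lesions may be flare.

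The cost is a protocol clarification and a short SAP addition. A few patients may have one further scheduled scan, which footnote l already requires, and rPFS will be slightly shorter in the sensitivity analysis.
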